7.1 Study design

7.1.1 Description of study design

This study has been designed as an observational, multi-center registry to collect efficacy and safety data in Ph+ ALL pediatric patients (ages 1 to <18 years old) treated with chemotherapy + imatinib, with or without hematopoietic stem cell treatment (\pm HSCT) primarily in European countries. The study concept was endorsed by the EMA as part of the post-marketing commitment EMEA/H/C/000406/II/80 and the design is aligned with ensuing discussions, as well as current medical practice in the treatment of newly diagnosed Ph+ ALL in pediatric patients across Europe.

A minimum of 50 pediatric patients meeting eligibility criteria after informed consent signature will be enrolled into the registry primarily from European countries, with some limited recruitment from non-EU countries, e.g. Russia, Ukraine. Due to the descriptive nature of this registry and the lack of a specific hypothesis to be tested, no formal sample size calculation exists. Medical feasibility is ongoing, although enrollment in Europe is estimated at a rate of 20 patients per year (or less). Enrollment may be supported through cooperation with approved, clinical trials (e.g. EsPhALL Study). The EsPhALL Study is an ongoing Phase II/III, open label, randomized study designed to compare safety and efficacy of imatinib with chemotherapy in pediatric patients with Ph+/BCR-ABL+ acute lymphoblastic leukemia. The trial is registered with EudraCT (2004-001647-30) and clinicaltrials.gov - number NCT00287105.

The registry will capture an observational follow-up period of minimum 5 years for each enrolled patient, or such information until early patient discontinuation (Section 7.1.4), as measured from the date of start of imatinib treatment. For the period whilst the database is open, retrospective additions to or revisions of the entered data will be possible at any time as additional or corrective data emerges. For patients meeting all inclusion criteria, enrollment is defined as having occurred on the date of patient inclusion into the registry (i.e. signature of informed consent).

No prospective clinical, instrumental or laboratory assessments/ interventions will be performed other than those required for disease management according to local best practice or locally approved summary of product characteristics or as stipulated in a clinical trial protocol, if a patient is taking part in a clinical trial in parallel with this registry (e.g. EsPhALL Study).

The population will include patients at different stages of chemotherapy + imatinib treatment upon their enrollment into this registry (Section 7.2.1). For the purposes of this registry, and in order to achieve its objectives, the notions of "baseline" and "follow-up" are entirely independent of the timing/ date of patient registry enrollment.

- The notion of "baseline" will consist of patient pre-treatment information from the time of diagnosis until just prior to start of treatment with imatinib.
- The notion of "follow-up" information will comprise any data collected by the treating physician and/ or designee from the start of imatinib onwards (i.e. post-"baseline"), regardless of whether this was prior to or after the date of registry enrollment.

Patient follow-up visits (whether prior to or after registry enrollment) will be scheduled according to the standard practice of the site and to the treating physician's best judgment or as specified in the visit schedule of any clinical trial in which the patient may be or may have been enrolled. Where disease evaluation is performed frequently, any follow-up information collected that is relevant to the objectives of this registry should be recorded in the database. Data will be collected such that the observational follow-up for long term safety and efficacy will be a minimum 5 years for each enrolled patient or such available data until early patient discontinuation.

Efficacy assessments will include standard long-term outcomes such as Overall Survival (OS) and Event Free Survival (EFS) (Section 7.4.2.3). Minimal Residual Disease (MRD) will be assessed at appropriate time points (Section 7.4.2.5). In terms of long-term safety, adverse events and serious adverse events in the observation period will also be collected.

Disease management, disease status and therapeutic interventions will be recorded. Follow-up will capture patient and disease status, response to treatment and treatment/ regimen changes at a frequency defined by the standard practice of each site.

Designated registry staff will enter the data into an electronic Case Report Forms (eCRFs) through a web-based internet system using fully validated software that conforms to regulatory requirements for electronic data capture. For each patient enrolled in this registry a minimum of a once yearly update of data in the registry database must occur (12 ± 2 month intervals).

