7.2.2 Inclusion Criteria

Patients eligible for inclusion in this registry have to meet **all** of the following criteria:

- 1. Male or female, pediatric patients aged greater than 1 year (≥365 days) and less than 18 years old (<17 years, 365 days) at diagnosis.
- 2. Documented, newly diagnosed Philadelphia Chromosome-positive (Ph+) acute lymphoblastic leukemia (ALL).
 - Recorded presence of t(9;22)(q34;q11) is required e.g. determined via institutional cytogenetics or FISH and/ or of the presence of BCR-ABL fusion transcript identified by RT-PCR or FISH.
- 3. Enrolled into this registry within 6 months of diagnosis or enrolled in a clinical trial within 6 months of diagnosis, although no earlier than Jan-2012.
- 4. Previously treated or currently on treatment with any chemotherapy regimen + imatinib (of an HA-approved formulation or HA-approved Glivec[®] generic) ± HSCT.
- 5. Written informed consent obtained prior to any information being entered into the registry (parent / legal guardian consent, where applicable).
 - Assent from a patient enrolled as a minor by parent / legal guardian consent **must** be obtained wherever possible. Obvious child dissent **must** be respected.
 - A patient enrolled as a minor by parent / legal guardian consent **must** be re-consented as an adult upon reaching the legal age of maturity during the course of the registry (legal age of maturity defined by local regulations).
 - Patients fulfilling the inclusion criteria, but who have died prior to registry opening and without the opportunity to give consent, may still be eligible for inclusion, subject to local requirements regarding the consent process.

The registry participating physician must assess whether there are any third-party agreements limiting the clinical trial patient's data collection as part of the non-interventional study given that no identification of proprietary treatment information will take place.

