7.2.4 Reasons for non-inclusion

The reasons for non-inclusion in the registry will be recorded during pre-screening and classified as:

- Did not meet diagnostic criteria
 - Patients for whom the presence of t(9;22)(q34;q11) could not be determined/ confirmed or for whom diagnosis occurred outside of the specified age range or for whom diagnosis was greater than 6 months before first treatment.
- Subject consent not given (e.g. either by parent/ legal guardian or subject themselves)

- Alternative treatment choice (e.g. physician's decision not to treat with imatinib or to treat with a non-HA-approved, Glivec[®] generic).
- Unknown
- Other (please specify)

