7.7.1 Analysis sets

The Full analysis set (FAS) comprises all patients who received at least one dose of imatinib + chemotherapy in the observational period.

The Safety set consists of all patients who received at least one dose of imatinib and with a valid post-baseline assessment. The statement that a patient has no AE constitutes a valid safety assessment. The occurrence of a death also constitutes a valid safety assessment. The safety set will be the population used in the assessments of safety. Patients with no post-baseline safety assessment will be listed.

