7.7.4.1 Primary endpoint

The **primary endpoint** will be event-free survival (EFS) considering the following events: relapse at any site, development of a second malignant neoplasm or death.

Event free survival is defined as the time from diagnosis to the earliest of these events.

Censoring date will be the date of last contact for patients who did not experience any of these events.

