7.7.4.2 Main secondary endpoints

The main secondary efficacy endpoint will be overall survival (OS).

OS is defined as the time from diagnosis to death from any cause.

Censoring date will be the date of last contact for patients who are still alive.

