8.5 Informed consent procedures

Eligible patients may only be included in the registry after providing written (witnessed, where required by law or regulation), IRB/IEC/REB-approved informed consent or, if incapable of doing so, after such consent has been provided by a legally acceptable representative of the patient. In cases where the patient's representative gives consent, the patient should be informed about the registry to the extent possible given his/her understanding. If the patient is capable of doing so, he/she should indicate assent by personally signing and dating the written informed consent document or a separate assent form.

According to local regulations, any child under the age of consent (for that region) must get consent from the legal guardian. Where applicable, children should also provide 'assent' after being provided with appropriate information about the registry (age of assent determined by the ethics committee or local requirements).

Informed consent must be obtained before any registry data is collected. The process of obtaining informed consent should be documented in the patient source documents. The date when a subject's Informed Consent was actually obtained will be captured in their CRFs.

Novartis will provide to participating physicians, in a separate document, a proposed informed consent form (ICF) that is considered appropriate for this registry and complies with the ICH GCP guideline and regulatory requirements. Any changes to this ICF suggested by the participating physicians must be agreed to by Novartis before submission to the IRB/IEC/REB, and a copy of the approved version must be provided to the Novartis monitor after IRB/IEC/REB approval.

If applicable and according to local regulations, the physician must explain to each patient (or legally authorized representative) the nature of the registry, its purpose, the requirement to report SAEs to Novartis per ICH guidelines, and the expected duration. Each patient must be informed that participation in the registry is voluntary and that he/ she may withdraw from the program at any time and that withdrawal of consent will not affect his/her subsequent medical treatment or relationship with the treating physician.

9 Management and reporting of adverse events/adverse reactions

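### EFS and OS run from diagnosis, but entry needs imatinib and usually later consent; deaths after registry opening and before consent are not provided for, so both curves lean upwards

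*Protocol*

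**What the plan says.** **Time origin.** Section 7.7.4.1: "Event free survival is defined as the time from diagnosis to the earliest of these events". Section 7.7.4.2: "OS is defined as the time from diagnosis to death from any cause". Both are censored at last contact, and 7.7.4.4 describes them by Kaplan-Meier without mentioning delayed entry or a landmark.

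**Conditions for being analysed.** The full analysis set is "all patients who received at least one dose of imatinib + chemotherapy in the observational period" (7.7.1). Enrolment is the date of consent (7.1.1). A directly enrolled patient must enter within 6 months of diagnosis. A trial-route patient must have entered the trial within 6 months of diagnosis, no earlier than January 2012, and the lag to registry consent has no limit (7.2.2). Data collection started on 14 July 2014, and enrolment was still open at Amendment 2 in 2017 (Section 3).

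**Time before enrolment.** Baseline and follow-up "are entirely independent of the timing/ date of patient registry enrollment" (7.1.1), so data from before consent count.

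**Safeguards.** Section 7.2.1 names the selection risk and promises every effort to obtain data on all eligible EsPhALL patients from January 2012, including the dead, subject to guardian consent and local rules. Section 7.2.2 says that patients "who have died prior to registry opening and without the opportunity to give consent, may still be eligible for inclusion", again subject to local requirements. Section 8.5 says, with no matching exception: "Informed consent must be obtained before any registry data is collected". The non-inclusion log in 7.2.4 includes patients "for whom diagnosis was greater than 6 months before first treatment", whereas the criterion in 7.2.2 concerns time from diagnosis to registry or trial enrolment.

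**The concern.** Time between diagnosis and entry is counted as time at risk, although a death in that interval can keep the patient out of the analysis. The interval from diagnosis to first imatinib is free of death for every analysed patient. The interval to consent is free of death unless a rule brings the deceased patient back in, and that rule is worded only for deaths before registry opening. A child who died after opening but before consent, on either route, has no explicit way in.

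The resulting error is systematic and favourable. It affects the primary endpoint and the main secondary endpoint of a registry that the EMA requested because these outcomes rested on limited data (5.1). Section 7.9 does not list it among the limitations.

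**Working it through.** The protocol derives no figure that could be reproduced (7.5 gives no sample size calculation), so what follows is an illustration of size.

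**Inputs from the protocol.** 48-month EFS 69.6% and OS 83.6% (5.3.1). Longest direct-route lag: 6 months (7.2.2). January 2012 to 14 July 2014 is about 2.5 years; January 2012 to Amendment 2 in early 2017 is about 5 years.

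**Assumptions.** Lags are uniform over the stated range, every pre-consent death is missed, and follow-up is otherwise complete to 5 years. The yearly rates are a = 0.0706 (event-free to relapse), b = 0.02 (event-free to death, assumed) and c = 0.271 (relapse to death).

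**Model.** With h = a + b = 0.0906 and k = a/(c − h) = 0.0706/0.1804 = 0.391:
- EFS(t) = exp(−ht)
- OS(t) = (1 + k)exp(−ht) − k exp(−ct)

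At 4 years, EFS = exp(−0.3624) = 0.696 and OS = 1.391 × 0.696 − 0.391 × 0.338 = 0.836, which match 5.3.1. At 5 years the true values are EFS 0.6357 and OS 0.7836.

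**Bias.** If a patient is included only when death falls after the lag L, the ordinary curve from diagnosis estimates EFS(5)/mean OS(L) and OS(5)/mean OS(L). The divisor is OS for both endpoints because entry requires being alive, not event-free.

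| Lag (years) | mean OS(L) | EFS read as | OS read as |
|---|---|---|---|
| 0 to 0.5 | 0.9943 | 0.639 (+0.4 points) | 0.788 (+0.4) |
| 0 to 2.5 | 0.9608 | 0.662 (+2.6) | 0.816 (+3.2) |
| 0.5 to 5 | 0.8946 | 0.711 (+7.5) | 0.876 (+9.2) |

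If half of the missed deaths are recovered in the middle row, the divisor becomes 1 − 0.0392/2 = 0.9804 and the bias falls to +1.3 (EFS) and +1.6 (OS).

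**Sensitivity to the timing of deaths.** A constant death hazard fitted to the same OS rate places more deaths early. True 5-year OS is then 79.9%. The ordinary estimate is 80.8% for lags of 0 to 6 months and 84.6% for 0 to 30 months, a bias of 0.9 and 4.7 points. Delayed entry gave 80.1% and 80.0%.

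**Imatinib interval alone.** The protocol does not state its length. Under the same constant hazard, an assumed gap of one month moves 48-month OS from 83.6% to 83.9% and EFS from 69.6% to 69.9%.

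**Precision.** At n = 50 the 95% half-width at 48 months is 1.96 × √(0.696 × 0.304/50) = 12.8 points for EFS and 1.96 × √(0.836 × 0.164/50) = 10.3 points for OS.

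**Cost of delayed entry.** In the three-state model at n = 50 with lags of 0 to 2.5 years, delayed entry removes the bias, but the standard deviation of 5-year EFS rises from about 6.6 to about 10 points. The root mean square error rises from about 7 to about 10. About 3.4 of 17 EFS events precede consent and drop out. With lags of 0.5 to 5 years nobody is at risk before 0.5 years, so some bias remains unless the curve starts there.

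**The case against.** Much of the case against this point stands, and it limits the point in five ways.

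- A reader might infer that patients enter only if alive at consent. Sections 7.2.1 and 7.2.2 contradict that: some deceased patients are admitted, and all eligible EsPhALL patients since January 2012 are sought. The gap is narrower. The exception stops at registry opening, the recovery effort names only EsPhALL, and both depend on local rules.
- A reader might infer that 8.5 bars the data of all deceased patients. It does not, because it accepts consent from a legally acceptable representative. What conflicts is its unqualified sentence against the no-consent exception in 7.2.2.
- A reader might infer that the non-inclusion log cannot show these patients. It has categories for consent not given and for other reasons, so they can be logged but not identified reliably.
- For EFS only death is protected. A relapse or second malignancy before consent in a living patient is recorded and counts (7.1.1).
- Delayed entry might seem the natural primary analysis. At n = 50 its extra variance outweighs the bias removed for EFS in the settings above.

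It can also be said that 7.7 leaves detail to a reporting analysis plan that is not at hand, that Kaplan-Meier does not rule out a delayed-entry risk set, that 7.7.4.4 already plans subgroups by enrolment into clinical studies, and that restriction to imatinib-treated patients fits the objective. All fair. But an analysis plan cannot recover patients whom the consent rule keeps out, nor repair the log. The subgroup split separates the routes without correcting either.

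**Conclusion.** The point holds in this limited form. The direction is upwards for OS and for the death component of EFS. The size is not known, because the protocol gives no route mix, lag distribution or count of early deaths. With every pre-consent death missed, the three-state model gives under 0.5 points at 5 years for consent within 6 months, and about 2.6 (EFS) to 3.2 (OS) points for lags of 0 to 2.5 years. A constant death hazard gives somewhat more for OS (0.9 and 4.7). Lags reaching 5 years could give 7.5 to 9 points, but only if no deceased patient is recovered, which 7.2.1 and 7.2.2 are written to prevent in part. For direct entrants the bias is trivial beside the sampling error. For late trial-route consent it can be a material fraction of the interval half-width, and it always favours the treatment.

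**What to change.** 1. **7.2.2:** extend the decedent exception from deaths before registry opening to deaths before consent could be obtained, for trial-route and direct-entry patients, subject to local requirements. Align 8.5 with it.
2. **7.2.4:** add a category for death before consent, and make the 6-month criterion match 7.2.2.
3. **7.7.4.4:** add a sensitivity analysis of EFS and OS with delayed entry. Time zero stays at diagnosis, and a patient joins the risk set at the later of imatinib start and consent. Where a cohort was captured completely regardless of vital status, use imatinib start as entry for the whole cohort. Start the curve where patients are at risk.
4. **7.9:** state that the primary curves may be biased upwards, and why.

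The cost is a few sentences of protocol text and one further analysis. The dates of diagnosis, first imatinib dose and consent are already collected (7.3.1.9, 7.4.2.1, 8.5). The delayed-entry intervals will be clearly wider at n = 50, so this analysis stands beside the primary one and does not replace it.

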7.1.2 Rationale for registry design

The study objective is to provide additional data to support the positive benefit-risk profile of imatinib in newly diagnosed pediatric Ph+ ALL patients. ALL is a common malignancy in the pediatric population but Ph+ ALL only accounts for up to 5% of pediatric ALL, which makes it a rare disease. Therefore, the conduct of multiple or large clinical trials in this patient population is not feasible. In addition, considering the remarkable benefit shown by the addition of imatinib to chemotherapy in Study COG-AALL0031 (Schultz et al. 2009), newly diagnosed Ph+ ALL pediatric patients have been treated with imatinib in clinical practice for some time and a prospective randomized trial with a "no imatinib" arm would be unethical in this patient population.

The NI-PASS registry design has been requested by EMA. In such, the medicinal product, imatinib, should be prescribed in a usual manner, according to the terms of the marketing authorization. The therapeutic strategy assigned to the patient is not proscribed by this registry protocol, but should fall within current medical practice. In order to clearly separate the decision to prescribe medication from the decision to include a given patient in this registry, there will be no central provision of medication. In summary, given the rarity of the disease, current clinical practice and unfeasibility of a randomized design, an observational study in

imatinib-treated patients is the optimal way to obtain prospective data in a standardized manner and address the study objective. A registry design permits the large scale capture of information across a sizeable international cohort of pediatric patients with newly diagnosed Ph+ ALL, producing a representative dataset without bias towards demographic or social characteristics.

7.1.3 Timing of interim analyses / study status reporting

Per EMA agreement, a study status update of the registry will be provided annually for the duration of the study. A final analysis will be performed after registry end of study.

7.1.4 Definition of the end of study

The end of study is defined as the point when a minimum of 5 years of observational followup data are available for each enrolled patient, or such available data until early discontinuation (Section 7.2.5), as measured from the date of start of imatinib treatment.

7.2 Setting

7.2.1 Population

The study population will include male or female pediatric patients (ages 1 to < 18 years) with documented, newly diagnosed Ph+ ALL, who enrolled into this registry within 6 months of diagnosis or were enrolled in a clinical trial within 6 months of diagnosis (although no earlier than Jan-2012), and who were previously treated or are currently on treatment with chemotherapy + imatinib \pm HSCT.

Data from patients participating in past or present interventional or observational studies can be included in this registry. Any concurrent participation of pediatric patients from Ph+ ALL studies is subject to the aforementioned studies' alignment with the inclusion criteria listed in Section 7.2.2. Any specific criteria in the concurrent clinical trial protocol explicitly excluding a patient from participating in a registry would render the patient ineligible for this registry. Enrollment of patients into this registry from the EsPhALL Study has been discussed with and endorsed by EMA.

The enrollment of patients already on treatment when entering the registry population introduces the risk of selection bias, since such patients may have different characteristics to those who progressed and died before registry opening. As a consequence, every effort will be made to obtain data for this registry from all patients meeting the inclusion criteria, who enrolled in the EsPhALL Study from Jan-2012 onwards. This would include patients who may have died before registry opening, although this is subject to parent/ legal guardian consent and local regulations. Any chemotherapy regimen in combination with imatinib is permissible.

The investigator or designee must ensure that only patients who meet all of the following inclusion criteria are enrolled in the study.

